### **Statistical Analysis:**

Data will be analyzed using mixed effects model [12; 27; 35]. This approach provides more information and therefore, more power compared to cross-sectional analyses, which focus on the analysis of one summary index, or more traditional analytic approaches such as a change score, end-point or repeated measures analysis of variance. In this approach, the repeated measures over time for each individual subject form a trajectory that can be described by a relatively simple model with a few parameters, such as intercept (baseline value) and slope (rate of change). With repeated measures, repeated observations within subjects are potentially correlated for any impact on the resulting tests of significance [34]. When this within subject correlation is properly incorporated, the repeated measures analysis takes full advantage of all information obtained from each subject, thereby greatly increasing the statistical power over methods that compare treatments cross-sectionally [23]. This approach can model for the differential patterns over the repeated assessments, instead of the totals at one point. As a result, this analytical approach increases the reliability of the measurement of response (since the slope combines repeated measures, which cancel much of the error of measurement), and will increase the protection against the major effects of missing data. In addition, the influence of missing data is reduced since it maximizes the number of subjects by allowing the inclusion of subjects with missing data, dropouts or those who are terminated early in the study without relying on data imputation procedures. The investigators will use pattern-mixture models to assess if there is any bias due to drop out or missing data. These will result in

increased power to detect effects and precision for the estimation of the effect sizes without requiring increased sample size, and provide the study with a uniform method of data analysis for all hypotheses that include multiple measurements from the same subjects. The mixed effects model method provides an estimate of the individual variability around the population trend, the variability of the individual intercepts (baseline values) and slopes (changes across time), and the correlation between them. A fully saturated treatment by time model will be utilized for inference. Co-variance structure will be chosen based on Akaike's Information Criterion (AIC). This allows for any group level effects to be incorporated into the model. Denominator degrees of freedom will be calculated using the Kenward-Roger small sample correction. Analyses will be conducted within and across nested levels of the study design; this will involve within-subject analyses (comparison of occasions of measurement nested within an individual), as well as between-subject analyses (comparison of two groups). In addition, any treatment group comparison can be adjusted for subject-specific characteristics and adjustments for changes in these characteristics over the course of the study, and incorporated into the single-subject analyses. Based on investigators' experience with previously completed studies, we expect a dropout rate of 10 to 20% throughout the study. All analyses will be two-tailed, where applicable, with  $\alpha = .05$ . Correction for family-wise Type I error rates will be made using the Westfall-Young randomization maxT procedure, which adjusts p-values for significance while taking into account the correlation of the outcomes [70]. In this way we can control for an overall family-wise error rate of .05 while achieving more power than Bonferroni adjustments.

**Hypothesis #2:** Active rTMS at LMC provides significantly more improvement in quality of life, mood and functions than sham LMC stimulations.

Independent Variables: Treatment Groups with two levels (Groups A & B), Visits with 8 levels: pre-treatment (Visit 2), treatment (Visits 7 & 12), and Post-treatment (Visits 13, 14, 15, 16, 17).

Dependent Variables: Attention (CPT II), Memory (Hopkins Verbal Learning Test) Execute function (Trail Making Test A and B, and Stroop Test), Hamilton Depression Scale, SF-36 and BPI.

Statistical Analysis: Data will be analyzed similar to hypothesis 1 and we estimated to have a minimum power of 85% for these analyses using similar method described above.

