## PTSD and MTBI

[figure not shown]
**Headache, MTBI and Post-traumatic Stress Disorder (PTSD) can be co-morbid conditions [51; 78]. Therefore, the potential benefits of rTMS in relieving PTSD related symptoms have been assessed in the investigators' previous studies related to rTMS and MTBI-HA. While in both studies (one published, one in preparation)[43], the investigators found patients with MTBI-HA on average consists of a slightly elevated score in the Clinician Administered PTSD Scale (CAPS), the majority of the individual scores and their overall average score did not meet the clinical diagnostic criteria of PTSD. In addition rTMS did not appear to have a significant impact in either improving or worsening their overall CAPS scores. Therefore, while patients will be screened for PTSD, the current proposed study will primarily focus on the stated specific aims. However, screening the study cohort's baseline (pre-treatment) PTSD severity will allow the investigators to conduct analyses if necessary with built-in covariates should the baseline CAPS scores are significantly different (although not expected) between the two proposed study groups.**

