## **VI). Process of randomization and treatment double blinding**

The un-blinded study biostatistician, [name], will create a list of patient identification numbers with randomized treatment assignments (A = Active/Real, B = Sham) using the SPSS software prior to the start of the study subject recruitment. Blocked randomization will be used with random block size of 3 or 6. Separate lists (up to 12) of replacement patient identification numbers will also be created so that replacement patients are assigned the same treatment as patients they are replacing. Patients will be randomized to study treatment groups in a 1:1 ratio. [name] will be contacted by the study coordinator with subjects' unique master ID number (sequential number, independent from any protected health information or any other identification source) and their descriptive information. After a subject signs the study consent, the study coordinator will be provided with that subject's randomization code. A minimization random assignment procedure will be used to match subjects on four variables: 1) mechanisms of injury; 2) gender; 3) severity of headache, and 4) past failed therapies for their headache. The minimization random assignment procedure aims to obtain equal numbers of subjects at the different levels of each matching variable. In contrast to stratified randomization, which aims for equal numbers of subjects in each treatment for every possible combination of the interested variables, the minimization method restricts its aim to equalizing treatment numbers at the different levels of each variable taken separately [20; 77]. Essential for this study, the procedure allows sequential assignment of subjects. This method has been shown to be superior to both simple and

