For hypotheses 1 and 2, where multiple analyses are conducted, correction for family-wise Type I error rates will be made using the Westfall-Young randomization maxTprocedure, which adjusts p-values for significance while taking into account the correlation of the outcomes [76]. In this way, the study can control for an overall family-wise error rate of .05 while achieving more power than Bonferroni adjustments. Using this method of power analysis, the investigators estimated a sample size of 128 (64 per group, accounted for a 20% dropout rate) provides the study with 85% power

to detect a medium effect size (RMASS program provided by Hedeker) [25; 26]. Medium effect sizes were used based on the results included in the above sections. Medium effect size is defined as a between-group difference increasing linearly from 0 at baseline to .5 SD units at the last time point. The minimum power estimation is based on sample size calculation for 10% and 20% attrition, correlations of 0.2, 0.5, and 0.8 between the repeated measures, and for medium and large effect sizes. Data will be analyzed using SPSS version 23, all analyses will be two-tailed, where applicable with  $\alpha = .05$ .

**Hypothesis #1:** Active rTMS at LMC provides significantly more reduction in headache intensity, duration and frequency of exacerbation than sham rTMS.

Independent Variables: Treatment Groups with two levels (Groups A & B), Visits up to 8 (See below). Dependent Variables: Primary outcome: Average daily headache assessments (B1, B2, B3, B4, B5, B6); Secondary outcome: Debilitating Headache Composite Score (B1, B2, B3, B4, B5, B6); M-VAS Scores of headache (Visits 2, 7, 12, 13, 14, 15, 16, 17); HTL-6 and NSI (Visits 2,13,14,15, 16, 17); headache rescue medication usage (Visits 2,13, 14, 15,16, 17). Note, not all variables are collected at all visits.

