**Exploratory aims:**

- 1) Explore the treatment effect on resting state supraspinal functional connectivity;
- 2) Explore moderators' effect of injury mechanisms (blast and non-blast) and the headache severity on the treatment outcomes.

Effect of treatment on the resting state supraspinal functional connectivity will be explored by using Self-organizing Group Level Independent Component Analysis (SogICA)[15; 28]. Primary focus will be placed on the medioprefrontal cortices (MPFCs) and the anterior cingulate cortex (ACC) regions, which were found to have altered functional connectivity in the MTBI patients in comparison to healthy controls in a recently published study conducted by the investigators [44]. These regions will serve as the primary seeded regions for subsequent pre- and post-treatment between-group ANCOVA resting state functional connectivity analyses. Additional levels of exploratory analyses will also include baseline between-group assessments with and without factoring in the mechanisms of injury and headache severities. For exploratory aim #2, the Injury mechanism (blast vs. non-blast) will be explored by adding it as independent variables to the mixed model. The effect of initial headache severity (Visit 2) will be explored by adding this baseline outcome to the mixed model as a fixed covariate.

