### Additional Inclusion Criteria:

1. male or female age between 18 to 65;
2. no prior experience of TMS treatment;
3. average persistent headache intensity more than 30 on the 0-100 mechanical visual analog scale(M-VAS) at the screening visit (visit 1)[64] and average persistent headache intensity score greater than 3/10 on a numerical rating scale (NRS) reported in the headache diary (between visits 1&2);
4. no history of daily persistent headache prior to the MTBI incidence:

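### The confirmatory mixed model leaves the baseline means unconstrained and fixes no covariate unconditionally, so precision available from data already collected is not secured

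*Combined protocol and SAP*

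**What the plan says.** For Hypothesis #1, Section 9 (Data Management, Analysis and Power Calculations) gives the model as "Independent Variables: Treatment Groups with two levels (Groups A & B), Visits up to 8 (See below"). The primary outcome is the diary average over B1 to B6. The other outcomes start at Visit 2, and Hypothesis #2 names pre-treatment Visit 2 as one of eight visit levels. B1 to B6 are not defined one by one. B1 appears to be the diary period between Visits 1 and 2, which is the pre-treatment period.

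Under Statistical Analysis the plan says: "A fully saturated treatment by time model will be utilized for inference". It states no constraint on the baseline means. The same section says that "any treatment group comparison can be adjusted for subject-specific characteristics", without naming a variable or a rule.

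Injury mechanism and baseline headache severity enter the model only under the exploratory aims, where severity "will be explored by adding this baseline outcome to the mixed model as a fixed covariate". Yet the randomisation section says: "A minimization random assignment procedure will be used to match subjects on four variables". These are injury mechanism, gender, headache severity and past failed therapies. One conditional covariate appears in the Background (PTSD and MTBI), where the investigators may "conduct analyses if necessary with built-in covariates should the baseline CAPS scores are significantly different" between the groups.

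**The concern.** When baseline is an outcome level with a free mean in each arm, each treatment-by-visit term is the between-arm difference in change from baseline (exactly so with complete data). The chance baseline difference is subtracted in full, which is more than needed unless baseline and follow-up are very highly correlated. Randomisation makes the true baseline means equal. A model that uses this, or that conditions on baseline, has smaller variance at every correlation the plan lists if the SDs are equal over time.

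Two things are at stake. The comparison is less precise than the collected data allow. In addition, an adjustment that is permitted but not listed carries a risk that covariates are chosen after the data are seen. The four allocation factors raise the same point: they were thought important enough to balance on, but they are absent from the confirmatory model.

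**Working it through.** **Inputs.** All are from Section 9, Data Management, Analysis and Power Calculations, unless marked.
- 64 per arm with 20% dropout: n = 64 × 0.8 = 51.2 per arm.
- Six diary periods, t = 0 to 5.
- Effect: "a between-group difference increasing linearly from 0 at baseline to .5 SD units at the last time point", so the mean difference is 0.5 × t/5.
- Correlations ρ = 0.2, 0.5, 0.8; two-sided alpha 0.05.
- Assumptions: B1 is baseline, compound symmetry, unit SD at every period, normal approximation, no maxT penalty.

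**Reproducing the stated 85%.** Take the linear contrast c = t − 2.5.
- Signal: δ = c'μ = 1.75.
- Variance per arm: c'Vc = 17.5(1 − ρ).
- z = δ/√(2 × variance/51.2), and power = Φ(z − 1.96).
- At ρ = 0.5 the variance is 8.75, z = 2.99 and power is 84.9%, which agrees with the stated figure. At 0.2 and 0.8 the same calculation gives 65.8% and 99.7%.

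**Same contrast, adjusted for baseline.** The variance becomes c'Vc − (c'V₁)²/V₁₁, where V₁ is the baseline column of V and V₁₁ the baseline variance. At ρ = 0.5, c'V₁ = −2.5 × (1 − 0.5) = −1.25, so the variance is 8.75 − 1.5625 = 7.1875, z = 3.30 and power is 91.0%.

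**Change at the last period.** The unadjusted variance is 2(1 − ρ) and the adjusted variance is 1 − ρ². At ρ = 0.5 these are 1.00 and 0.75, with z = 2.53 and 2.92.

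| Contrast | ρ | Power, as planned | Power, adjusted | Variance ratio |
|---|---|---|---|---|
| Linear | 0.2 | 65.8% | 80.0% | 1.40 |
| Linear | 0.5 | 84.9% | 91.0% | 1.22 |
| Linear | 0.8 | 99.7% | 99.8% | 1.08 |
| Last-period change | 0.2 | 51.6% | 73.3% | 1.67 |
| Last-period change | 0.5 | 71.6% | 83.2% | 1.33 |
| Last-period change | 0.8 | 97.9% | 98.8% | 1.11 |

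For the linear contrast, the adjusted analysis has the precision of an unadjusted one with 51.2 × ratio = 71.7, 62.3 and 55.1 completers per arm. The 5-df test of the whole treatment-by-time interaction also gains: at ρ = 0.5, about 62% rises to 76% (chi-square approximation).

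**Narrower baseline spread.** Entry requires "average persistent headache intensity score greater than 3/10 on a numerical rating scale (NRS) reported in the headache diary (between visits 1&2"), which may truncate the baseline distribution. Assume that the baseline SD is k = 0.8 of the later SD; the documents give no value.
- Linear contrast: 71.6/88.9/99.8% rises to 80.0/91.0/99.8% (ratios 1.23/1.08/1.00).
- Last-period change: the unadjusted variance is k² + 1 − 2ρk = 1.32/0.84/0.36, against 0.96/0.75/0.36 adjusted (ratios 1.38/1.12/1.00). At ρ = 0.5, power goes from 78.8% to 83.2%.

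At ρ = 0.8 and k = 0.8, change from baseline is already the optimal adjustment and nothing is gained or lost.

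**The case against.** The strongest reply is that nothing is broken. The planned test is valid, and change from baseline already uses the baseline value. The gain almost vanishes at a correlation of 0.8 and is about 2 points for the linear contrast at 0.5 if the baseline SD is narrowed as assumed above. The plan does not name the tested contrast, and the linear one was used here because it reproduces 85%. That match needs six periods, correlation 0.5 and 20% loss from the start; with the 36% dropout quoted under Research Design (about 41 per arm) the same calculation gives 76.4%.

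These points limit the size of the gain but leave its direction unchanged. The linear, last-period and omnibus tests all improve, or at worst stay level. Range restriction may also lower the correlation, which would increase the gain.

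The adjustment sentence can fairly be read as a general remark on what mixed models can do. On that reading the plan has no adjustment at all, and the fix is the same. The Background does name baseline CAPS and a trigger, so it would be wrong to say that no covariate is mentioned anywhere. That trigger is a baseline significance test and is tied to no particular analysis. The data management text on summarising potential covariates settles only how they might be represented.

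The allocation wording is also inconsistent: Research Design speaks of stratifying on two factors, and the randomisation section describes both blocks and minimization. Both places nevertheless list the same four factors for assignment.

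**Conclusion.** The concern holds as a gap in efficiency and pre-specification. It does not affect validity. With equal SDs and about 51 completers per arm, the planned model has 8% to 40% more variance than a baseline-adjusted one on the linear contrast, and 11% to 67% more on last-period change, across the plan's own correlations. At 0.5 this is about 6 points of power on the linear contrast and 12 on last-period change; at 0.8 it is about 1 point or less.

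The figures rest on B1 being baseline, compound symmetry, 20% loss from the start and no multiplicity penalty. The documents do not say which correlation applies, and the further gain from the minimization factors cannot be computed from them.

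**What to change.** For every confirmatory outcome with a baseline value, pre-specify one of two forms:
- baseline as a covariate with a baseline-by-visit interaction, and only post-baseline values (B2 to B6, or the post-baseline visits) as outcomes; or
- the present saturated model with both arms constrained to a common baseline mean.

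Add the minimization factors as fixed main effects, without visit interactions. Define the levels of past failed therapies, and of headache severity where it is entered as a category. Severity may be represented by the continuous baseline where that is the same measure. Replace the permissive adjustment sentence with this fixed list, and define B1 to B6. Compute the Westfall-Young maxT statistics from the same model. Decide now whether baseline CAPS is included, without a baseline significance test.

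The cost is SAP wording. With six diary periods, the covariate form adds about 5 baseline-by-visit parameters and at least 3 main effects. The common-baseline form has 11 mean parameters, one fewer than the present 12, before the main effects. All variables are already collected at baseline or for minimization.

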#### Research Design:

A total of 200 will be consented and 128 (64 per group, accounted for 36% dropout rate) patients will be randomized to be stratified based on their injury mechanisms (blast, non-blast) and headache severities (mild, moderate, severe) and enrolled over 6 years from VASDHS, and Naval Medical Center San Diego (MNCS). Patients meeting study enrollment criteria will be randomized into one of the two study groups (A&B) based on their mechanisms of injury, gender, severity of headache, and past failed therapies for their headache. The overall study duration for each subject is about 14 weeks developed into three phases according to the following schedule:

- 1) PRE-TREATMENT PHASE (weeks 1-2) consists of Visit 1 (Screening Visit) and Visit 2 (Pre-treatment Assessments);
- 2) TREATMENT PHASE (week 3-4) consists of Visits 3-12 (Neuronavigation guided rTMS consisting of 10 weekday treatments at  $>24$  and  $< 72$  hours apart, weekends excluded, maximum 5 weeks for treatment completion) rTMS will take place in Building 23 Room 105 at the VASDHS; and

3) POST-TREATMENT PHASE (week 5-14) consists of two initial weekly visits (Visits 13&14) and two additional biweekly visits (Visits 15&16) and one monthly visit (Visit 17).

Brain anatomical and functional MRI will be performed within 72 hours after Visits 2 and 13. Subjects will be required to fill out headache diary between assessment visits. Headache assessments along with quality of life, mood and functions assessments will be carried out at Visits 1,2, and 13--17. This frequency of treatment and duration of follow-up is in line with recently published rTMS articles related to TBI, headache and pain, and also in accordance with the 3-month post treatment initiation follow-up guideline /recommendation [32; 55; 80].

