### **Assessment Based Visits – Pre-treatment assessments (V2a), Post-TX 1-week (V13a), Post-TX 2-week (V14), Post-TX 4-week (V15), Post-TX 8-week (V16) and Post-TX 12 week (V17)**

Pre and post-treatment assessments will be conducted over video call, and questionnaires to be completed by subjects will be provided prior to each visit through MyHealtheVet or mailed to the subjects. Subjects will be given the choice to either: 1) complete questionnaires within 24hours of their video appointment and

return them through MyHealtheVet or FAX; or 2) complete them during the video call where subjects will provide their verbal responses and the study coordinator will document the response. The following assessment will have changes on administration:

1. Mechanical Visual Analogue Scale (MVAS) of Headaches, Muscle, and Joint Pain: subjects will rate their pain on the 0-100 MVAS scale at all On-site visits

The following assessments will not be conducted as they require in-person administration:

1. Stroop Test
2. Eye Tracking Assessment
3. Conner's Performance Test II
4. Trail Making Test

These assessments are part of the secondary hypothesis, measuring attention and executive functioning. Though these functions will not be measured, the primary aim of this study is to assess headache and quality of life and assessments related to the primary aim will still be administered.

All other assessments listed in the protocol will be administered with no changes, other than being conducted remotely. Subjects will continue to keep a daily log of their headaches and medication usage throughout the course of the study which will be collected by either sending it through MyHealtheVet or through FAX.

The following table summarizes the assessments/questionnaires administered:

Visit		2	2	3-	1	1	1	1	1
		a	b	12	3	3	4	5	6
					a	b			
Location		T	O	O	S	T	O	T	T
		H	S		H	S	H	H	H
Brief Pain Inventory-Short Form (BPI)	Self-administered		x		x		x	x	x
Neurobehavioral Symptoms Inventory (NSI)	Self-administered		x		x		x	x	x
		x		x	x		x	x	x

Headache Impact Test (HIT-6)	Self-administered					
Short Form Health Survey-36	Self-administered	x	x	x	x	
Hopkins Verbal Learning Test (HVLT)	Study Coordinator	x	x	x	x	
Hamilton Rating Scale for Depression (HRSD)	Study Coordinator	x	x	x	x	
Clinician-Administered PTSD Scale (CAPS-5)	Study Coordinator	x	x	x	x	
Modified Fatigue Impact Scale	Self-administered	x	x	x	x	
MVAS – Sliding Scale	Study Coordinator	x x	x	x	x	

TH: Telehealth; OS: On-site

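### The 85% minimum power claimed for Hypothesis 2 is not the minimum over the plan's own grid; at correlation 0.2 and 20% attrition it is about 66–70% (six occasions) or 74–79% (eight)

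*Combined protocol and SAP*

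**What the plan says.** The sample-size statement is in Section 9, Data Management, Analysis and Power Calculations: "a sample size of 128 (64 per group, accounted for a 20% dropout rate) provides the study with 85% power" for a medium effect. The effect is specified: "Medium effect size is defined as a between-group difference increasing linearly from 0 at baseline to .5 SD units at the last time point". The range of scenarios follows: "The minimum power estimation is based on sample size calculation for 10% and 20% attrition, correlations of 0.2, 0.5, and 0.8" between the repeated measures, for medium and large effects. Tests are two-tailed at 0.05, with a Westfall-Young maxT correction across outcomes.

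For Hypothesis 2, the Statistical Analysis text says "we estimated to have a minimum power of 85% for these analyses" and refers back to that method.

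Three related statements affect the calculation:

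- **Occasions.** The Hypothesis 2 text lists "Visits with 8 levels: pre-treatment (Visit 2), treatment (Visits 7 & 12") plus Visits 13 to 17. Research Design says that "quality of life, mood and functions assessments will be carried out at Visits 1,2, and 13--17", which gives six occasions if Visits 2 and 13–17 are counted.
- **Contributing patients.** The COVID-19 section on assessment-based visits says "The following assessments will not be conducted as they require in-person administration". The tests listed include CPT II, Trail Making and Stroop, all Hypothesis 2 outcomes.
- **Dropout.** Research Design ties the 128 randomised (64 per group) to a 36% dropout rate, the power section ties the same 128 to 20%, and the Hypothesis 1 analysis text says "we expect a dropout rate of 10 to 20% throughout the study".

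**The concern.** A minimum over a grid has to hold in its least favourable cell. Here that is the medium effect with correlation 0.2 and 20% attrition. For a difference that grows over time, a lower within-patient correlation means a noisier trend and less power, so one sample size cannot give the same power at correlations of 0.2 and 0.8. A single 85% called a minimum therefore needs checking.

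The documents give no expected correlation, so a reader cannot place the trial on the grid. If the true correlation is near the low end, the chance of missing a medium effect on a Hypothesis 2 outcome is about 30–34% (six occasions) or 21–26% (eight), not 15%. A null result could then be taken as evidence against a medium effect when the trial had limited ability to detect one.

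**Working it through.** **Inputs from the plan:** 64 per arm, 1:1 allocation; difference rising linearly from 0 to 0.5 SD; two-sided 0.05; correlations 0.2, 0.5, 0.8; attrition 10% and 20%; T = 6 or 8 occasions.

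**Assumptions (not in the plan):** compound symmetry with SD 1, equal spacing, linear group-by-time contrast, no multiplicity adjustment. The last favours the plan, because maxT can only lower these figures.

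**Formulas.** With t = 0, …, T−1:

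- contrast weights c_t = t − mean(t), and mean difference μ_t = 0.5·t/(T−1)
- signal Σc_tμ_t = 0.5·Σc_t²/(T−1)
- variance with n per arm throughout = 2(1−ρ)Σc_t²/n
- power = Φ(signal/SE − 1.96)

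For T = 6, Σc_t² = 17.5 and the signal is 1.75. For T = 8, Σc_t² = 42 and the signal is 3.00. With 20% lost throughout, n = 64 × 0.8 = 51.2.

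**Reproducing the 85%.** T = 6, ρ = 0.5: variance = 2 × 0.5 × 17.5/51.2 = 0.342, SE = 0.585, z = 1.75/0.585 = 2.99, power = Φ(1.03) = 84.9%. The plan's figure therefore matches the middle correlation with six occasions, which is also the number of diary periods (B1–B6) for the primary outcome.

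**The least favourable cell, ρ = 0.2.**

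- T = 6: variance = 2 × 0.8 × 17.5/51.2 = 0.547, SE = 0.740, z = 2.37, power = Φ(0.41) = 65.8%.
- T = 8: variance = 2 × 0.8 × 42/51.2 = 1.3125, SE = 1.146, z = 2.62, power = Φ(0.66) = 74.5%.

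Spreading the dropout linearly to the last visit, with variance 2ΣΣc_ic_jσ_ij/√(n_in_j), raises these to 70.4% and 78.8%. Generalised least squares with the same dropout gives 69.6% and 78.1%.

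**Full grid, medium effect** (completers only to gradual dropout):

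| Occasions | Attrition | ρ = 0.2 | ρ = 0.5 | ρ = 0.8 |
|---|---|---|---|---|
| 6 | 10% | 71–73% | 89–90% | over 99% |
| 6 | 20% | 66–70% | 85–88% | over 99% |
| 8 | 10% | 79–81% | 94–95% | over 99% |
| 8 | 20% | 74–79% | 91–94% | over 99% |

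Even with no attrition (n = 64), ρ = 0.2 gives only 75.4% (six) or 83.3% (eight). At 20% attrition, 85% needs a correlation of about 0.45–0.50 (six) or 0.32–0.39 (eight). With a large effect, taken as 0.8 SD by assumption, six occasions at ρ = 0.2 and 20% attrition give about 97–98%. The grid minimum is therefore the medium-effect cell.

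**Sensitivity, six occasions, 20% attrition.**

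- AR(1) covariance with a generalised-least-squares slope: 49–54%, 46–50% and 59–64% at lag-1 correlations 0.2, 0.5 and 0.8.
- Visit spacing from the COVID-19 schedule (weeks 0, 3, 4, 6, 10, 14, assuming two weeks of treatment) with compound symmetry: 63–67% at ρ = 0.2 and 83–85% at ρ = 0.5.
- Bonferroni across seven Hypothesis 2 outcomes at ρ = 0.2: about 37–42% (47–53% with eight occasions). The maxT result would lie between this bound and the unadjusted figure.

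**The case against.** The strongest objection is that the covariance form, contrast and spacing behind the 85% are not given, so any recalculation is conditional. That is true of the exact percentages. Three other readings deserve a fair hearing.

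1. **A slope model with baselines constrained equal** gives 90–91% (six) or 94–95% (eight) at ρ = 0.2 and 20% attrition. It fits the effect definition, which starts from zero at baseline, and the general talk of intercepts and slopes. But the analysis text specifies a saturated treatment-by-time model for inference and describes no baseline constraint.
2. **64 per group may mean completers.** Two successive 20% losses make 36% (1 − 0.8 × 0.8), and 200 × 0.64 = 128, which would tie the dropout figures together. With 80 randomised per arm and 20% attrition, ρ = 0.2 gives 83–87% with eight occasions, so the claim would roughly hold. With six it gives 75–80%. Research Design says that 128 are randomised, which goes against this reading.
3. **The minimum may be over outcomes, not over the grid.** This is possible, but the power section itself applies the term to the range of attrition and correlations.

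It is also fair that Hypothesis 2 is not the primary hypothesis and that a confidence interval would limit over-reading. What stands is that the percentages are conditional. None of these readings has enough support in the text to rescue the figure.

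**Conclusion.** The claim is wrong as written. With 64 randomised per arm, 85% is not the minimum over the correlations and attrition rates that the plan names. The shortfall in the least favourable cell is about 15–19 percentage points with six occasions and 6–11 with eight, and some shortfall remains with no attrition. The sizes rest on compound symmetry, equal spacing, a linear contrast and unadjusted alpha. AR(1) and multiplicity correction lower them further; an equal-baseline slope model would remove the shortfall.

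The 85% for the primary outcome is not itself called a minimum and is reproducible at a correlation of about 0.5. The fault there is only that its dependence on the correlation, the contrast and the alpha is not stated.

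**What to change.** Keep N = 128 and the analysis as planned.

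1. In the power section, state the correlation, number and spacing of occasions, covariance form, attrition pattern, contrast and alpha (before or after maxT) behind the 85%. Report power at each correlation in the plan's grid from a rerun of the sponsor's own calculation.
2. In the Hypothesis 2 text, delete the word minimum or restate the figure from that rerun. First reconcile the eight listed visits with the assessment schedule, and state how many patients are expected to contribute to CPT II, Trail Making and Stroop under the COVID-19 design.
3. Reconcile the 36%, 20% and 10–20% dropout statements. Say whether 64 per group is randomised or completing, and whether 36% is loss between consent and randomisation (128/200 = 64% retained).

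The cost is one rerun and wording changes in four places, with no extra patients. The drawback is that the stated power becomes less favourable.
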